5.8 EXPLORATORY ANALYSES

Exploratory Analyses will be performed on the Full Analysis Set.

Exploratory Analyses for Clinical Endpoints

Change from baseline in ADCOMS, ADAS-Cog, CDR-SB, MMSE, and FAQ across all clinical assessment time points not included in primary, key secondary or secondary analysis will be summarized by visits. The MMRM described in [Section 5.4.1.2](#) will be used to analyze change from baseline in ADCOMS, ADAS-Cog, CDR-SB, MMSE, and FAQ across all clinical assessment time points not included in primary, key secondary or secondary analysis. The analysis will be performed with/without censoring as described in [Section 5.4.1](#).

Exploratory Analyses for Biomarkers

Scatter plots including the Spearman correlation coefficient will be produced for change from baseline in vMRI values (total hippocampal volume, right and left hippocampal, whole brain, and total ventricular volumes) and change from baseline in amyloid PET values (SUVR of global cortical average with reference region of subcortical white matter, whole cerebellum, whole cerebellum mask, whole cerebellum adjusted by subcortical white matter, cerebellar grey matter, and composite reference consisting of cerebellar cortex, pons, subcortical white matter and cerebellar white matter) at 12 and 18 months.

Change from baseline at 12 and 18 months in PET SUVR, volumetric MRI and CSF biomarkers will also be analyzed by baseline PET SUVR subgroups (\geq median and $<$ median). The median here is the median baseline value among all subjects.

Change from baseline in brain amyloid levels as measured by amyloid PET SUVR of global cortical average with other reference regions at 12 and 18 months will also be explored. Some other PET data parameters may also be analyzed. The amyloid PET SUVR of global cortical average with whole cerebellum as reference region and subcortical white matter as longitudinal adjustment factor can be derived as follows ([Landau et al, 2015](#)):

- 1) For each visit, the global cortical average (Ctx) is first normalized to the whole cerebellum ($WhCereb$) at the same visit:

$$\text{Baseline: } Ctx_{BL}^* = \frac{Ctx_{BL}}{WhCereb_{BL}}$$

$$\text{At post baseline visit } v_i: Ctx_{v_i}^* = \frac{Ctx_{v_i}}{WhCereb_{v_i}}$$

- 2) For each visit, calculate the ratio below for subcortical white matter (*WM*):

$$\text{Baseline: } WM_{BL}^* = \frac{WM_{BL}}{WhCereb_{BL}}$$

$$\text{At post baseline visit } v_i : WM_{v_i}^* = \frac{WM_{v_i}}{WhCereb_{v_i}}$$

- 3) The normalized global cortical average in 1) is then scaled by the ratio of subcortical white matter in 2).

$$\text{Baseline: } SUVR_{BL} = \frac{Ctx_{BL}^*}{WM_{BL}^* / WM_{BL}^*} = Ctx_{BL}^*$$

$$\text{At post baseline visit } v_i : SUVR_{v_i} = \frac{Ctx_{v_i}^*}{WM_{v_i}^* / WM_{BL}^*}$$

- 4) Finally, the change from baseline at post baseline visit v_i is:

$$\Delta SUVR = SUVR_{v_i} - SUVR_{BL}$$

After some simple algebra, it can be shown that the $SUVR_{v_i}$ in 3) can be written as follows:

$$\text{Baseline: } SUVR_{BL} = Ctx_{BL}^* = \frac{Ctx_{BL}^*}{WM_{BL}^* / WM_{BL}^*} = \frac{Ctx_{BL}^*}{WM_{BL}^*} \cdot \frac{WM_{BL}}{WhCereb_{BL}}$$

$$\text{At post baseline visit } v_i : SUVR_{v_i} = \frac{Ctx_{v_i}^*}{WM_{v_i}^* / WM_{BL}^*} = \frac{Ctx_{v_i}^*}{WM_{v_i}^*} \cdot \frac{WM_{BL}}{WhCereb_{BL}}$$

Therefore this SUVR is essentially the SUVR of global cortical average with subcortical white matter as reference region multiplied by the ratio of subcortical white matter and whole cerebellum at baseline.

Exploratory Analyses to Investigate the Relationship between Clinical Endpoints and Biomarkers

Clinical endpoints to be investigated include ADCOMS and CDR-SB. Biomarkers to be investigated include CSF ($A\beta$ 1-42, t-tau and p-tau), vMRI (total hippocampal volume, right and left hippocampal, whole brain, and total ventricular volumes), and PET values (SUVR of global cortical average versus the various reference regions).

The relationship between baseline biomarker values and change from baseline in clinical endpoints at 12 or 18 months will be investigated as follows:

- An MMRM will be fitted with dependent variable of change from baseline in clinical endpoints at 12 months and covariates of baseline clinical endpoints, treatment group, visit, randomization stratification variables (i.e., clinical subgroup [MCI due to AD, Mild Alzheimer's Disease Dementia], the presence or absence of ongoing AD treatment

[AChEIs or memantine or both], APOE ϵ 4 carrier status [positive, negative]), region, treatment group-by-visit interaction, and baseline CSF (as continuous variables). The model will be repeated using baseline vMRI and baseline amyloid PET values to replace baseline CSF respectively.

- The above analyses will also be performed for change from baseline in clinical endpoints at 18 months and baseline values of CSF, vMRI and amyloid PET values.
- The same analyses will be done with baseline CSF, baseline vMRI and baseline amyloid PET values being categorized into two groups: \geq median, $<$ median. The median here is the median baseline value among all subjects.

The relationship between change from baseline in biomarker values and change from baseline in clinical endpoints at 12 or 18 months will be investigated as follows:

- A scatter plot by treatment group will be made between change from baseline in clinical endpoints at 12 months and change from baseline in each of the biomarkers at 12 months, respectively: CSF, vMRI and amyloid PET values. A Spearman correlation coefficient with its p-value will be displayed in each scatterplot.
- The same analyses will also be performed for change from baseline in clinical endpoints, CSF, vMRI and amyloid PET values at 18 months.
- A longitudinal plot of mean change in clinical endpoints over time (baseline, 12 months, 18 months) by treatment group and subgroups defined by change from baseline in CSF, vMRI and PET values (\geq median, $<$ median) will also be produced. Summary statistics will also be provided.

The relationship between change from baseline in clinical endpoints and change from baseline in biomarkers at 18 months may also be evaluated using an ANCOVA model within treatment group as appropriate. Changes from baseline in clinical endpoints at 18 months will be the response variables and either continuous or categorical change of biomarkers will be independent variables. The ANCOVA model will also include baseline value of clinical endpoint as a covariate, randomization stratification variables as factors, and other terms as appropriate.

Proportion of subjects who have become amyloid negative during study will also be summarized by treatment groups. Summary of clinical endpoints will be presented for those subjects who remain amyloid positive and subjects who change from amyloid positive to amyloid negative by visual read at either 12 months or 18 months of treatment. Time to conversion from amyloid positive to amyloid negative may also be analyzed.

Additional analyses will also be performed whereby PET SUVR values are converted to the Centiloid scale ([Klunk, et al., 2015](#)).

Only subjects that have data in both clinical endpoints and each individual biomarker at specified timepoints will be included in these respective analyses.

Exploratory Analyses for Japanese Subjects

The primary efficacy endpoint (ADCOMS) and its components, ADAS-cog, CDR-SB and MMSE across all clinical assessment time points between BAN2401 and placebo in Japanese subjects with EAD will be evaluated using the descriptive statistics within Japanese subjects as well as compared with the overall study population.

Additional subgroup analysis in safety and baseline characteristics for Japanese subjects will be performed based on the needs of drug development in Japan.

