3.1.4 Exploratory Objectives

1. To evaluate the effects of BAN2401 compared to placebo on clinical status across all clinical assessment time points not analyzed in Key Secondary and Secondary sections in subjects with EAD by assessment of:
 - a. ADCOMS
 - b. Clinical Dementia Rating – Sum of Boxes (CDR-SB)
 - c. Mini Mental State Examination (MMSE)
 - d. Functional Activities Questionnaire (FAQ)
 - e. Alzheimer’s Disease Assessment Scale – Cognitive Subscale (ADAS-Cog)
2. To explore the relationship between change from baseline in clinical status at 12 and 18 months of treatment and baseline brain amyloid pathophysiology as measured by amyloid PET in subjects with EAD
3. To explore the relationship between change from baseline in clinical status and change from baseline in brain amyloid pathophysiology at 12 and 18 months of treatment in subjects with EAD as measured by amyloid PET
4. To explore efficacy of BAN2401 compared to placebo and the overall study population on the ADCOMS across all clinical assessment time points in Japanese subjects with EAD
5. To characterize the population pharmacokinetics (PK) of BAN2401 in EAD subjects, and to examine the effect of intrinsic and extrinsic factors on the PK

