5.4.1.2 Conventional Analyses

Statistical methods for the conventional analyses of primary efficacy endpoint will use a mixed effects model with repeated measures (MMRM) comparing placebo to the identified ED₉₀ dose from the Bayesian analysis. The model will include baseline ADCOMS as covariate, with treatment group, visit, randomization stratification variables (i.e., clinical subgroup [MCI due to AD, Mild Alzheimer's Disease Dementia], the presence or absence of ongoing AD treatment [AChEIs or memantine or both], *APOE4* status [positive, negative]), region, treatment group-by-visit interaction as fixed effects. If there is an imbalance across treatment groups based on randomization stratification variables, additional MMRM model will be run without the randomization stratification variables. In addition, ANCOVA model will also be used with treatment as a factor and baseline value as a covariate.

An unstructured covariance matrix will be employed in the MMRM to model the covariance of within subject effect. These analyses will be performed using all randomized subjects in the full analysis set as well as in the per protocol set. There will be no conventional analysis at each interim analysis before early success is claimed and as such there will be no multiplicity adjustment made to account for the interim analyses. In case of early success, the conventional analyses will be performed using the data collected prior to the interim analysis as well as at the end of 12 months assessment, and the analysis at the end of 12 months assessment will be considered as sensitivity analysis to the analysis at early success.

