8.1 DEFINITION OF VISIT WINDOWS

The protocol specified visits/weeks and corresponding time windows used for visit-wise analyses are presented in terms of days relative to the first dose. For subjects that are randomized, the last available assessment on or before the date of the first dose of study drug will be used as the Baseline-Day 1.

Different assessment may have different visit schedule. A general rule for determining a time window for each scheduled visit is to split the two consecutive scheduled visits in the middle point of the two consecutive visits. For example, the time window for visit X is from the middle

point between visit (X-1) and X (exclusive) to the middle point between visit X and (X+1) (inclusive). According to protocol, “assessments should take place on the first day of the study visit in the designated study week except as noted below (footnotes h, i, and j pertaining to imaging assessments, and footnote o pertaining to CSF sample collection)” (see [page 96, Protocol Amendment 08](#)). Therefore, the scheduled day corresponding to scheduled visit at week Y is $((Y-1)*7+1)$ days. For example, the scheduled day for scheduled visit at weeks 1, 3, and 5 are Day 1, Day 15, and Day 29, respectively and the corresponding time window for scheduled visit at weeks 1 and 3 are [Day 1, Day 8] and [Day 9, Day 22], respectively

For scheduled every 3 months post baseline efficacy assessments, the analysis visits are the same as the scheduled visits. Any window rules will not apply. This is per ITT principle and also assumes that the actual assessment dates are independent from any other factors or are random and centered at scheduled time point.

For Early Termination (ET) visit and Follow Up (FU) visit, the following rules apply for efficacy assessment:

- If the last scheduled 3-month assessment before early termination (LS), ET assessment and FU assessment are in three separate sequential 3-month windows, e.g., Window(x), Window (x+1) and Window(x+2), then the analysis visits for last scheduled 3-month assessment (LS), ET assessment and FU assessment will be x, x+1 and x+2, respectively.
- If both LS and ET are in Window(x) and FU is in Window(x+1) [note: this is the most likely situation since ET and FU are expected to be separated by 3 months], then analysis visit is x for LS (per rule 1.) and (x+1) for FU and ET will not be included in Bayesian analyses and MMRM analyses.

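### The Section 5.8 model for baseline biomarkers gives one slope common to all visits, not the slope at month 12 or month 18 that the analysis sets out to examine

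*SAP*

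**What the plan says.** The second exploratory objective in SAP Section 3.1.4 is tied to two time points: "To explore the relationship between change from baseline in clinical status at 12 and 18 months of treatment and baseline brain amyloid pathophysiology". Section 5.8 extends it to CSF and vMRI and opens: "The relationship between baseline biomarker values and change from baseline in clinical endpoints at 12 or 18 months will be investigated as follows".

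The model is introduced with "An MMRM will be fitted with dependent variable of change from baseline in clinical endpoints at 12 months". Its listed terms are the baseline clinical score, treatment group, visit, the three stratification factors, "region, treatment group-by-visit interaction, and baseline CSF (as continuous variables". The vMRI and PET measures replace CSF in turn.

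Two repeats follow with no change of terms. For the later time point: "The above analyses will also be performed for change from baseline in clinical endpoints at 18 months". For the median split: "The same analyses will be done with baseline CSF, baseline vMRI and baseline amyloid PET values being categorized into two groups". No biomarker-by-visit term appears in any of the three.

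**The concern.** In most MMRMs a main-effect covariate is a nuisance adjustment, and leaving out its interaction with visit does little harm. Here the biomarker coefficient is itself the answer to the objective. A main effect forces that coefficient to be the same at every visit in the model, so no month-12 or month-18 slope can be read from the fit. The plan allows treatment effects to vary by visit but not the effect that this analysis exists to measure.

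Change from baseline is zero for everyone at the start. In a progressive disease it is natural, though not certain, that an association with baseline pathology is small at first and grows. A common slope then mixes early and late visits. Across several biomarkers, several PET reference regions and two clinical endpoints, a diluted slope could be reported as absence of a relationship at 18 months.

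**Working it through.** The SAP states no sample size, power or effect for this analysis, so there is no figure to reproduce. The sizes below are illustrative.

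**Inputs from the SAP**
- Visits every 3 months (Section 8.1: "For scheduled every 3 months post baseline efficacy assessments, the analysis visits are the same as the scheduled visits"), so months 3-12 (k = 4) or 3-18 (k = 6).
- Unstructured covariance (Section 5.4.1.2: "An unstructured covariance matrix will be employed in the MMRM"), taken to apply here too.
- Visit-to-visit correlation ρ = 0.8 (Appendix 13.2, section 8.1). The form is not given, so both AR(1) and compound symmetry (CS) are shown.
- Two-sided 10% level (Section 5).

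**Assumptions not in the SAP**
- The shape of the biomarker slope over visits, and the growth of the SD of change.
- 80% power for the test at the named visit, which sets its expected z at 1.645 + 0.842 = 2.486.

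**Formula.** With visit slopes b and residual covariance S, the main-effect coefficient estimates w′b, where w = S⁻¹1 / (1′S⁻¹1). Write r for w′b divided by the slope at the named visit, and v for the variance of the common slope relative to that visit's slope. The expected z is then 2.486 × r / √v, and power is approximately Φ(z − 1.645).

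**Equal SDs.**
- AR(1): the end visits get weight 1/(2 + 0.2(k − 2)) each and the inner visits 0.2 times that. v = 1.8/(2 + 0.2(k − 2)), which is 1.8/2.4 = 0.750 or 1.8/2.8 = 0.643.
- CS: equal weights. v = (1 + 0.8(k − 1))/k, which is 3.4/4 = 0.850 or 5/6 = 0.833.
- The weights are symmetric in both cases, so with linear growth the common slope is the slope at the mean visit time: r = 7.5/12 = 0.625 or 10.5/18 = 0.583.

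| Target | Correlation | r | z | Power (named-visit test: 80%) |
|---|---|---|---|---|
| 12 months | AR(1) | 0.625 | 2.486 × 0.625/√0.750 = 1.79 | 56% |
| 12 months | CS | 0.625 | 2.486 × 0.625/√0.850 = 1.69 | 52% |
| 18 months | AR(1) | 0.583 | 2.486 × 0.583/√0.643 = 1.81 | 57% |
| 18 months | CS | 0.583 | 2.486 × 0.583/√0.833 = 1.59 | 48% |

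A simulation with an estimated unstructured covariance (600 subjects, six visits, 2000 runs) agrees: mean ratio 0.58, and power 56.3% against 78.0% for the named visit.

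**Linear growth with SD rising over time.** Weight moves to the earliest visit, and late visits can get negative weight.

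| SD of change | AR(1), 12 / 18 months | CS, 12 / 18 months |
|---|---|---|
| 0.10 rising to 0.15 at the last visit | 0.35 / 0.37 | 0.06 / −0.13 |
| Proportional to √time | 0.23 / 0.18 | −0.03 / −0.16 |

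(Entries are r.)

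**Flat slopes, equal SDs.**
- Constant slope: r = 1.00 and power 85-93%, above the 80% of the named-visit test.
- Slope at 0.93 of its final value by month 3 and full from then on: r = 0.97-0.99 and power 84-92%.

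The plateau result needs the plateau to be reached by the first visit in the model. With a week-6 visit included at only 0.11 of the final slope, as in the appendix's symptomatic treatment profile, r for 12 months is 0.65 under AR(1) and 0.81 under CS.

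**The case against.** **Single-visit reading.** Section 5.8 names the response as change at 12 months, repeats the analysis for 18 months, and limits these analyses to subjects with data at the specified time points. If only one visit enters, the biomarker coefficient is already the slope wanted. However, visit and treatment-by-visit terms cannot be estimated from one visit, so that reading contradicts the listed model. The wording is ambiguous and does not rescue the specification.

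**Other analyses.** Section 5.3.4 plans MMRMs in the biomarker subgroups, which could show clinical change by visit in each half, but no comparison between halves is planned. Section 5.7 allows ad hoc work on baseline status and disease course. The scatter plots and ANCOVA later in Section 5.8 use change in biomarkers, not baseline values. None of these prespecifies the slope at month 12 or 18.

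**Stronger readings that the SAP does not support.**
- A reader might infer that the estimate is always biased toward zero and always loses more than 20 points of power. The SAP gives no time course for a biomarker slope. The profiles in Appendix 13.2 describe treatment effects, and one of the three is nearly flat from week 12. With a flat slope the specified model gains power.
- A reader might infer that a stated hypothesis is tested wrongly. The SAP speaks only of exploring and investigating, and states no null, alternative or power.
- A reader might infer that the 12- and 18-month answers must be the same number. That holds only if one model with all visits serves both questions, and Section 5.8 describes separate analyses.

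**Conclusion.** The point holds in conditional form. As listed, the Section 5.8 MMRM yields one covariance-weighted slope over the visits it includes and cannot yield the slope at month 12 or month 18, in either the continuous or the median-split version. This follows from the model terms and needs no numerical assumption.

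The size of the consequence does rest on assumptions. If the slope grows linearly with equal SDs and correlation 0.8, the estimate is about 0.6 of the target and power falls from 80% to 48-57%. With growing SDs the ratio ranges from about 0.37 down to −0.16, depending on the SD pattern and correlation form. If the slope is constant, or has plateaued by the first visit in the model, little or nothing is lost and the common-slope test is the stronger one. No treatment comparison, dose selection or success criterion depends on this analysis.

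**What to change.** In Section 5.8, restate the response as change from baseline at all scheduled post-baseline visits up to month 12 (or month 18). Add a baseline biomarker-by-visit interaction to the MMRM in both the continuous and median-split versions. Report and test the biomarker slope, or the difference between median groups, at month 12 and at month 18 by contrast. Alternatively, fit an ANCOVA at the named visit and drop the visit terms; this is simpler but does not use earlier visits from subjects who lack the later one.

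The interaction adds one parameter per visit beyond the first: three for months 3-12, five for months 3-18. No new data are needed. If the slope is in fact constant, the named-visit test gives up some power, 80% against 85-93% in the equal-SD illustration. Reporting the interaction alongside would show which case applies.

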5.2 STUDY SUBJECTS

5.2.1 Definitions of Analysis Sets

The number (percent) of subjects included in each analysis set will be presented by analysis set, treatment group and overall. The description of the analysis data sets are:

The Randomized Set is the group of subjects who are randomized to study drug.

The Safety Analysis Set is the group of subjects who receive at least 1 dose of study drug and have at least 1 post dose safety assessment.

The Full Analysis Set is the group of randomized subjects who receive at least 1 dose of study drug and have baseline and at least 1 post dose primary efficacy measurement.

The PK Analysis Set is the group of subjects with at least 1 quantifiable BAN2401 serum concentration with a documented dosing history.

The PD Analysis Set is the group of subjects who have sufficient PD data to derive at least 1 PD parameter.

The Per Protocol (PP) Analysis Set is the subset of subjects in the Full Analysis Set who complied with the protocol.

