5.3.5 Handling of Missing Data, Drop-outs, and Outliers

The missing primary endpoint will be imputed using Bayesian imputation method based on longitudinal model in the primary Bayesian analysis ([Section 5.4.2.2](#)). In the conventional analyses, the missing primary endpoint will be handled by the Mixed-effects Models for Repeated Measures (MMRM). Other statistical methods for missing data in conventional analyses may also be performed as sensitivity analyses. Missing values in key secondary endpoints, secondary endpoints and exploratory endpoints related to clinical assessments and biomarkers will be handled by the MMRM in the conventional analyses.

Efficacy Variables

If any item is missing within the Composite Score (ADCOMS), ADAS-cog, MMSE, CDR, and FAQ then their respective total scores will be missing.

CSF Biomarkers

Subjects with baseline values \geq ULOQ or \leq LLOQ will be excluded from all statistical analyses.

For analyses defined in [Section 5.8](#), only subjects with post-baseline values $>$ LLOQ and $<$ ULOQ will be included. For additional analyses, subjects with at least 1 post-baseline value,

including those \geq ULOQ or \leq LLOQ, will be categorized as follows: “stable”, “increased from baseline”, and “decreased from baseline”. For subjects that have numerical differences calculated, any increases will be categorized as “increased from baseline” and any decreases will be categorized as “decreased from baseline” regardless of magnitude. Difference of 0 will be categorized as “stable”. Subjects with baseline values $>$ LLOQ and $<$ ULOQ and post-baseline values \geq ULOQ will be categorized as “increased from baseline”, subjects with baseline values $>$ LLOQ and $<$ ULOQ and post-baseline values \leq LLOQ will be categorized as “decreased from baseline”.

When an improved assay becomes available, all samples may be re-run using the improved assay.

Adverse Events

Adverse events with missing severity will be assigned the highest severity. Adverse events with missing relationship will be assigned the highest relationship.

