6.0 ACCRUAL AND DROPOUT

We assume accrual will increase at a constant rate over the first 6 months of the study to a peak accrual rate of 32 patients per month. The table below shows the approximate accrual rate at each month during the 6 month ramp-up to the steady state accrual rate of 32 patients per month.

Accrual Ramp-Up: Patients per Month	
Week	Patients Per Month
1	5.33
2	10.66
3	16
4	21.33
5	26.66
6	32
Steady State Patients per Month from 6 Months	32

We assume an exponential rate of dropout such that 22% of patients have dropped out by 26 weeks and 40% have dropped out by 52 weeks. As a sensitivity analysis we also consider dropout rates of 20% and 30% by 52 weeks.

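### The closing inclusion rule in SAP 5.8 also catches the baseline-biomarker MMRMs and, read plainly, drops subjects without the 12- or 18-month clinical value, against 5.3.5 and the Full Analysis Set

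*SAP*

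**What the plan says.** Section 5.8 opens with the analysis set: "Exploratory Analyses will be performed on the Full Analysis Set". Section 5.2.1 defines that set as randomized, dosed subjects who "have baseline and at least 1 post dose primary efficacy measurement". No 12- or 18-month value is required.

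Under the heading on the relationship between clinical endpoints and biomarkers, 5.8 first plans models on baseline biomarkers: "An MMRM will be fitted with dependent variable of change from baseline in clinical endpoints at 12 months and covariates of baseline clinical endpoints". Treatment, visit, stratification variables, region, treatment-by-visit and the baseline biomarker are also in the model. It is then extended: "The above analyses will also be performed for change from baseline in clinical endpoints at 18 months". It is repeated once more with the biomarkers split at the median.

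The same part then plans analyses of change against change: scatter plots with Spearman coefficients, plots and summaries by biomarker change, and an ANCOVA. After paragraphs on amyloid status and the Centiloid scale it ends: "Only subjects that have data in both clinical endpoints and each individual biomarker at specified timepoints will be included in these respective analyses".

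Section 5.3.5 gives the general rule: "Missing values in key secondary endpoints, secondary endpoints and exploratory endpoints related to clinical assessments and biomarkers will be handled by the MMRM". The sentence goes on to confine this to the conventional analyses.

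**The concern.** An MMRM deals with dropout through the visits that a subject did attend before leaving. The baseline-biomarker models need the biomarker only at baseline. The timepoints that the text names for them are baseline for the biomarker and 12 or 18 months for the clinical endpoint. A rule that demands data at those timepoints therefore removes subjects who lack the late clinical value, together with their earlier visits. The model keeps the name MMRM but is fitted to completers.

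Two things are at stake. Data already collected are thrown away, so the biomarker coefficient is less precise. In addition, if leaving is related to earlier decline, the completers are a selected group and their mean decline differs from that of the Full Analysis Set.

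**Working it through.** **1. Passages side by side.**

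| Place | Who enters the baseline-biomarker MMRM |
|---|---|
| 5.8 opening, with 5.2.1 | Anyone with a baseline and one post-dose primary efficacy measurement |
| 5.3.5 | Missing exploratory clinical values are handled by the model |
| 5.8 closing sentence, plain reading | Only those with the baseline biomarker and the 12- or 18-month clinical value |

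The first two agree; the third does not.

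**2. Share affected.** The SAP has two dropout assumptions: 20% at 12 months, exponential (Section 4, vMRI), and "22% of patients have dropped out by 26 weeks and 40% have dropped out by 52 weeks" (Appendix 13.2, Section 6.0). Check of the second: 1 − 0.6^0.5 = 22.5% at 26 weeks, against 22% stated. Extending to 18 months with 1 − (1 − d)^1.5:

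| Dropout at 12 months | Without 12-month value | Without 18-month value |
|---|---|---|
| 20% | 20% (160 of 800) | 1 − 0.8^1.5 = 28.4% (228 of 800) |
| 40% | 40% (320 of 800) | 1 − 0.6^1.5 = 53.5% (428 of 800) |

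These are upper limits. Subjects who leave before any post-baseline visit have no visits to lose, and discontinuers who are followed may still have the late value.

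**3. Precision when dropout is unrelated to outcome.** The planned model has no biomarker-by-visit term, so one biomarker coefficient is shared by all visits. The information on it from a subject with k visits is proportional to i(k) = 1′V(k)⁻¹1, where V(k) is the covariance of the first k visits. Assume six 3-monthly visits (Section 8.1 describes 3-monthly efficacy assessments), a correlation of 0.80 (Appendix 13.2, Section 8.1) and, for a case that can be done by hand, equal variances and equal correlations. Then i(k) = k / (1 + 0.8(k − 1)), which gives 1, 1.1111, 1.1538, 1.1765, 1.1905 and 1.2.

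- All visits: the sum over k of S(k) × [i(k) − i(k−1)], where S(k) = (1 − d)^(3k/12) is the share still observed at visit k.
- Completers: S(6) × i(6).

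20% dropout, with S = 0.9457, 0.8944, 0.8459, 0.8, 0.7566, 0.7155:
- All visits: 0.9457 + 0.0994 + 0.0361 + 0.0181 + 0.0106 + 0.0068 = 1.1167.
- Completers: 0.7155 × 1.2 = 0.8586.
- SE ratio: √(1.1167 / 0.8586) = 1.14.

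40% dropout, with S = 0.8801, 0.7746, 0.6817, 0.6, 0.5281, 0.4648:
- All visits: 0.8801 + 0.0861 + 0.0291 + 0.0136 + 0.0074 + 0.0044 = 1.0207.
- Completers: 0.4648 × 1.2 = 0.5577.
- SE ratio: √(1.0207 / 0.5577) = 1.35.

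With correlation that decays between visits, or an SD that grows with the square root of time, the same formula gives 18-month increases of about 11-15% and 27-37%. The ceiling is 1/√S(6): 18% and 47%. For the 12-month model (four visits) the hand-worked case gives smaller increases: √(1.0993 / 0.9412) = 1.08 and √(1.0089 / 0.7059) = 1.20.

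**4. Mean decline when dropout depends on the last observed change.** This was simulated with a mean change of 0.12 at 12 months (CSD 0.03 divided by the stated 25%), SD 0.15 and correlation 0.80. The dropout mechanism is an assumption, not taken from the SAP. Error of the completer mean at 18 months:

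| Mechanism | 20% dropout | 40% dropout |
|---|---|---|
| Unrelated to outcome | none | none |
| Faster decliners leave, log hazard 0.4-0.7 per SD | −6 to −10% | −13 to −20% |
| Faster decliners leave, log odds 1 per SD | 0.1517 vs 0.1794, −15% | 0.1244 vs 0.1794, −31% |
| Slower decliners leave, log odds 1 per SD | 0.2077 vs 0.1794, +16% | 0.2351 vs 0.1794, +31% |

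Likelihood on all visits, with a separate biomarker slope at each visit, recovered the mean in every case.

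**5. Biomarker coefficient.** When the planned shared coefficient was fitted with faster decliners leaving, all subjects gave 0.0104-0.0113 and completers 0.0108-0.0116. The difference is small, and here it is not an understatement.

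**The case against.** The strongest reply is that the closing sentence is loose rather than wrong. It never says which timepoints it means, and it follows the change-on-change analyses, where it is plainly right. The visit and treatment-by-visit terms and the Full Analysis Set line both suggest a kinder reading: baseline biomarker plus any post-baseline clinical data. That reading would remove the conflict, but the text does not state it, and the timepoints that it does name for these models are 12 and 18 months.

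The 5.3.5 sentence is limited to conventional analyses, which could mean only the treatment comparisons of 5.4. It could equally mean anything non-Bayesian. Section 5.3.5 also sets its own CSF restriction for 5.8, so special rules for 5.8 are not foreign to it. This narrows the conflict with 5.3.5 but leaves the one with the Full Analysis Set.

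A reader might infer three stronger things that the documents do not support:

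- That the rule understates decline. The SAP does not say whether dropout depends on decline; the error vanishes or reverses under other mechanisms.
- That it weakens the estimated link with the biomarker. A slope specific to 12 or 18 months was attenuated by 9-18% in simulation under the strong dropout mechanism, but the plan fits one coefficient shared across visits, where the effect was small. For the same reason, keeping all subjects does not turn that coefficient into an 18-month slope.
- That every dropout is lost. Section 5.2.2 foresees efficacy follow-up after stopping treatment, and 8.1 assigns early-termination and follow-up assessments to analysis visits.

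**Conclusion.** The point holds as a contradiction in wording with a cost in precision. On its plain reading the sentence makes the baseline-biomarker MMRMs completer analyses, against the Full Analysis Set statement in 5.8 and the missing-data rule in 5.3.5. Up to 20-40% of subjects at 12 months and 28-54% at 18 months are affected under the SAP's own dropout assumptions. The 18-month standard error rises by about 11-15% or 27-37%, given 3-monthly visits and a correlation of 0.80. Bias in mean decline is possible in either direction and cannot be sized without the dropout mechanism. Bias in the shared biomarker coefficient is small and depends on the model.

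The analyses are exploratory and carry no decision rule. Primary and key secondary results are unaffected. Severity: minor.

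**What to change.** Limit the closing sentence to the paired change-on-change analyses: the scatter plots, the Spearman coefficients, the ANCOVA, and the plots or summaries by biomarker change. For the baseline-biomarker MMRMs, continuous and median-split, state that they include all Full Analysis Set subjects who have that baseline biomarker and at least one post-baseline value of the clinical endpoint, with all visits entered. A completer version may stay as an optional sensitivity analysis.

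The cost is one or two sentences in the SAP. No new data are needed, and visits already collected are used.
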